### 12.7.3 Health-related Quality of Life Endpoints

The Health Outcome/Quality of Life endpoints are the change from baseline in the following health outcome/QoL assessments at Weeks 12, 16, and 24:

- Quick Inventory of Depressive Symptomatology-Self Report (16 Items) (QIDS-SR16) total score. The total score (range 0-27) is calculated as the sum of the following 9 items: Highest score on any sleep items (Q1-Q4), Q5, highest score on any appetite/weight items (Q6-Q9), Q10, Q11, Q12, Q13, Q14, highest score on either psychomotor items (Q15 & Q16). The total score will be considered as missing if any of the component score is missing.
- The Dermatology Life Quality Index (DLQI) total score (0-30) will be calculated as the sum of 10 questions with each ranging from 0 to 3. The scoring of each answer is as follows:

Very much	Scored 3
A lot	Scored 2
A little	Scored 1
Not at all	Scored 0
Not relevant	Scored 0
Question unanswered	Scored 0
Question 7: "prevented work or studying"	Scored 3

If one question is left unanswered this is scored 0 and the scores are summed and expressed as usual out of a maximum of 30. If two or more questions are left unanswered the total DLQI score is missing. If question 7a is answered 'no' or 'not relevant', then the answer of 7b will be ignored. Additionally, the score of each of 6 domains (daily activities, personal relationships, symptoms and feelings, leisure, work/school, and treatment) will be summarized separately.

- The SF-12 summary scales will be calculated using the SF-12 Health Survey Standard Scoring software. Summary scores will be computed for Physical Summary (PCS) and Mental Summary (MCS). Subscores will also be computed for the following 8 domains:
  - Physical Functioning (PF)
  - Role-Physical (RP)
  - Bodily Pain (BP)

- Social Functioning (SF)
  - Mental Health (MH)
  - Role-Emotional (RE)
  - Vitality (VT)
  - General Health (GH)
- Work Productivity and Activity Impairment Questionnaire: Psoriasis (WPAI:PSO) score. WPAI-PSO outcomes are expressed as impairment percentages, with higher numbers indicating greater impairment and less productivity, i.e., worse outcomes as follows
    - The percent work time missed due to psoriasis will be summarized for all subjects who answer “Yes” to Question 1, “Are you currently employed?”. This will be calculated using the following formula:  $100 * ((\text{Question 2}) / (\text{Question 2} + \text{Question 4}))$
    - The percent impairment while working due to psoriasis will be summarized for all subjects who have worked at least 1 hour in the past 7 days (ie, response to Question 4 is greater than zero). This will be calculated as  $100 * (\text{Question 5} / 10)$
    - The percent overall work impairment due to psoriasis will be summarized for subjects who answer “Yes” to Question 1 and response >0 to Question 4. This will be calculated as  $100 * \{ \text{Question 2} / (\text{Question 2} + \text{Question 4}) + (1 - \text{Question 2} / (\text{Question 2} + \text{Question 4})) * \text{Question 5} / 10 \}$
    - The percent activity impairment due to psoriasis will be summarized for all subjects with a non-missing response to Question 6. This will be calculated as  $100 * (\text{Question 6} / 10)$ .

Any of the impairment percentage will be considered as missing if the contributing question is missing.

- Health Economics and Outcome Research (HEOR) evaluation. Responses to each of the following 3 questions will be summarized separately by visit:
  - Number of times to any physician’s office or urgent care clinic
  - Number of times to a nurse practitioner, a physician assistant, a psychologist, a naturopath, an acupuncturist, a chiropractor, or other healthcare professional (HCP)
  - Number of times received care from a health professional in your home

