Appendix 5 Quality of Life Assessment: Dermatology Life Quality Index (DLQI)

DERMATOLOGY LIFE QUALITY INDEX

DLQI

Hospital No:

Date:

Score:

Name:

Diagnosis:

Address:

The aim of this questionnaire is to measure how much your skin problem has affected your life OVER THE LAST WEEK. Please check one box for each question.

1.	Over the last week, how itchy, sore, painful or stinging has your skin been?	Very much A lot A little Not at all	   	
2.	Over the last week, how embarrassed or self conscious have you been because of your skin?	Very much A lot A little Not at all	   	
3.	Over the last week, how much has your skin interfered with you going shopping or looking after your home or yard ?	Very much A lot A little Not at all	   	Not relevant 
4.	Over the last week, how much has your skin influenced the clothes you wear?	Very much A lot A little Not at all	   	Not relevant 
5.	Over the last week, how much has your skin affected any social or leisure activities?	Very much A lot A little Not at all	   	Not relevant 
6.	Over the last week, how much has your skin made it difficult for you to do any sport ?	Very much A lot A little Not at all	   	Not relevant 
7.	Over the last week, has your skin prevented you from working or studying ?	yes no	 	Not relevant 
	If "No", over the last week how much has your skin been a problem at work or studying ?	A lot A little Not at all	  	

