### **12.8.3 Health-related Quality of Life Analyses**

All QoL endpoints will be summarized by visit and treatment group using descriptive statistics on the FAS population.

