Change from Baseline in DLQI Total Score by Visit  
Full Analysis Set, OC

	PPC-06 400 mg QD (N=XX)	PPC-06 400 mg BID (N=XX)	PPC-06 600 mg BID (N=XX)	Placebo (N=XX)
Baseline				
N	XX	XX	XX	XX
Mean (SD)	XX.X (XX.X)	XX.X (XX.X)	XX.X (XX.X)	XX.X (XX.X)
Median	XX	XX	XX	XX
Minimum, Maximum	XX, XX	XX, XX	XX, XX	XX, XX
Week 12				
N	XX	XX	XX	XX
Mean (SD)	XX.X (XX.X)	XX.X (XX.X)	XX.X (XX.X)	XX.X (XX.X)
Median	XX	XX	XX	XX
Minimum, Maximum	XX, XX	XX, XX	XX, XX	XX, XX
Change from baseline				
N	XX	XX	XX	XX
Mean (SD)	XX.X (XX.X)	XX.X (XX.X)	XX.X (XX.X)	XX.X (XX.X)
Median	XX	XX	XX	XX
Minimum, Maximum	XX, XX	XX, XX	XX, XX	XX, XX

<Repeat for Week 16, Week 24>

Note: DLQI= Dermatology Life Quality Index. OC= Observed Cases.

Generated on XX/XX/XX:XXXX by XXXXXX / Uses: XXXX / Reference: Listings XXXX

Table 14.2.3.2.2: Analysis of Quality of Life Outcome  
Change from Baseline in DLQI Individual Domains by Visit  
Full Analysis Set, OC

	PPC-06 400 mg QD (N=XX)	PPC-06 400 mg BID (N=XX)	PPC-06 600 mg BID (N=XX)	Placebo (N=XX)
Symptoms and Feelings				
Baseline				
N	XX	XX	XX	XX
Mean (SD)	XX.X (XX.X)	XX.X (XX.X)	XX.X (XX.X)	XX.X (XX.X)
Median	XX	XX	XX	XX
Minimum, Maximum	XX, XX	XX, XX	XX, XX	XX, XX
Week 12				
N	XX	XX	XX	XX
Mean (SD)	XX.X (XX.X)	XX.X (XX.X)	XX.X (XX.X)	XX.X (XX.X)
Median	XX	XX	XX	XX
Minimum, Maximum	XX, XX	XX, XX	XX, XX	XX, XX
Change from baseline				
N	XX	XX	XX	XX
Mean (SD)	XX.X (XX.X)	XX.X (XX.X)	XX.X (XX.X)	XX.X (XX.X)
Median	XX	XX	XX	XX
Minimum, Maximum	XX, XX	XX, XX	XX, XX	XX, XX
<Repeat for Week 16, Week 24>				
<Repeat for other domains: Daily Activities, Leisure, Personal Relationships >				

Note: DLQI= Dermatology Life Quality Index. OC = Observed Cases.

Generated on XX/XX/XX:XXXX by XXXXX / Uses: XXXX / Reference: Listings XXXX

Table 14.2.3.2.2: Analysis of Quality of Life Outcome  
 Change from Baseline in DLQI Individual Domains by Visit  
 Full Analysis Set, OC

	PPC-06 400 mg QD (N=XX)	PPC-06 400 mg BID (N=XX)	PPC-06 600 mg BID (N=XX)	Placebo (N=XX)
Work and School				
Baseline, n (%)				
Yes	XX (XX.X)	XX (XX.X)	XX (XX.X)	XX (XX.X)
No	XX (XX.X)	XX (XX.X)	XX (XX.X)	XX (XX.X)
Not relevant	XX (XX.X)	XX (XX.X)	XX (XX.X)	XX (XX.X)
Week 12, n (%)				
Yes	XX (XX.X)	XX (XX.X)	XX (XX.X)	XX (XX.X)
No	XX (XX.X)	XX (XX.X)	XX (XX.X)	XX (XX.X)
Not relevant	XX (XX.X)	XX (XX.X)	XX (XX.X)	XX (XX.X)
<Repeat for Week 16, Week 24>				

Note: DLQI= Dermatology Life Quality Index. OC = Observed Cases.

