1. Falling asleep; 2. Sleep during the night, 3. Waking up too early; 4. Sleeping too much 5. Feeling sad, 6. Decreased appetite, 7. Decreased appetite 8. Decreased weight (within the last two weeks), 9. Increased weight (within the Last two weeks), 10. Concentration/decision making, 11. View of myself, 12. Thoughts of death or suicide,13. General interest, 14. Energy level, 15. Feeling slowed down, 16. Feeling restless

[1] Study day is calculated relative to the date of first study drug administration (Day 1).

Generated on XX/XX/XX:XXXX by XXXXXX / Uses: XXXX

Listing 16.2.6.9.1: Dermatology Life Quality Index (DLQI) Individual Questions  
 All Randomized Subjects  
 [PPC-06 400 mg QD] [ PPC-06 400 mg BID] [ PPC-06 600 mg BID] [Placebo]

Subject Number	Analysis Visit	Visit Date (Day) [1]	Q1	Q2	Q3	Q4	Q5	Q6	Q7	Q8	Q9	Q10
XX-XXX	Baseline	DDMMMYYYY(XX)	X	X	X	X	X	X	X	X	X	X
	Week 12	DDMMMYYYY(XX)	X	X	X	X	X	X	X	X	X	X
	Week 16	DDMMMYYYY(XX)	X	X	X	X	X	X	X	X	X	X
	Week 24	DDMMMYYYY(XX)	X	X	X	X	X	X	X	X	X	X
	Etc.											

[1] Study day is calculated relative to the date of first study drug administration (Day 1).

Generated on XX/XX/XX:XXXX by XXXXX / Uses: XXXX

Listing 16.2.6.9.2: Dermatology Life Quality Index (DLQI) Domains and Total Score  
 All Randomized Subjects  
 [PPC-06 400 mg QD] [ PPC-06 400 mg BID] [ PPC-06 600 mg BID] [Placebo]

Subject Number	Analysis Visit	Visit Date (Day) [1]	Symptoms and Feelings		Daily Activities		Leisure		Work and School	Personal Relationships		Treatment	Total	
			Value	CFBL	Value	CFBL	Value	CFBL	Value	Value	CFBL	Value	Value	CFBL
XX-XXX	Baseline	DDMMYYYY(XX)	X	--	X	--	X	--	X	X	--	X	X	--
	Week 12	DDMMYYYY(XX)	X	X	X	X	X	X	X	X	X	X	X	X
	Week 16	DDMMYYYY(XX)	X	X	X	X	X	X	X	X	X	X	X	X
	Week 24	DDMMYYYY(XX)	X	X	X	X	X	X	X	X	X	X	X	X
XX-XXX	Baseline	DDMMYYYY(XX)	X	--	X	--	X	--	X	X	--	X	X	--
	Week 12	DDMMYYYY(XX)	X	X	X	X	X	X	X	X	X	X	X	X
	Week 16	DDMMYYYY(XX)	X	X	X	X	X	X	X	X	X	X	X	X
	Etc													

Note: CFBL=Change from baseline calculated as post-baseline minus baseline.

Symptoms and Feelings includes Q1 and Q2; Daily Activities includes Q3 and Q4; Leisure includes Q5 and Q6; Work and School includes Q7 and Q7a; Personal Relationships includes Q 8 and Q9; Treatment includes Q10

[1] Study day is calculated relative to the date of first study drug administration (Day 1).

Generated on XX/XX/XX:XXXX by XXXXX / Uses: XXXX

Listing 16.2.6.10.1: SF-12 Subdomains  
 All Randomized Subjects  

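### The DLQI scoring rule discards item 7b after a 'no' to 7a, the only case in which the form asks it, so two valid answers score 0 instead of 2 and 1

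*SAP*

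**What the plan says.** SAP 12.7.3 defines the DLQI total as the sum of 10 items, each scored 0 to 3, for a range of 0 to 30. Its answer table gives 3 for *Very much*, 2 for *A lot*, 1 for *A little*, and 0 for *Not at all*, *Not relevant* or unanswered. A positive answer to the first part of item 7 scores 3. One unanswered question scores 0; two or more make the total missing. The same section then adds: "If question 7a is answered 'no' or 'not relevant', then the answer of 7b will be ignored".

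The form is in Protocol Appendix 5. The first part of item 7 asks whether, in the last week, "has your skin prevented you from working or studying", with answers yes, no or not relevant. The second part is introduced by a condition, that the first answer was *No*, and then asks "over the last week how much has your skin been a problem at" work or study, with answers *A lot*, *A little* or *Not at all*.

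On reporting, SAP 12.7.3 says: "Additionally, the score of each of 6 domains (daily activities, personal relationships, symptoms and feelings, leisure, work/school, and treatment) will be summarized separately". The shell of Table 14.2.3.2.2 for "Work and School" has rows only for Yes, No and Not relevant. The note to Listing 16.2.6.9.2 states that "Work and School includes Q7 and Q7a". SAP 12.8.3 limits the analysis: "All QoL endpoints will be summarized by visit and treatment group using descriptive statistics on the FAS population".

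**The concern.** The rule and the form point in opposite directions. The form routes a subject to 7b only after *No*; the SAP throws 7b away after *No*. Followed exactly, the rule leaves no answer path on which 7b is scored.

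At stake is the DLQI total, whose change from baseline at Weeks 12, 16 and 24 is a named endpoint (Protocol 4.2.2) and supports the secondary objective on health-related quality of life. A subject whose skin did not stop work or study but caused a lot of difficulty there is recorded as having no work or study impairment.

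**Working it through.** **Inputs.** The scores 3, 2, 1 and 0 come from the answer table in SAP 12.7.3. The routing of item 7 comes from Protocol Appendix 5. The rule for 7b comes from SAP 12.7.3.

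**The plan's own figure.** The stated maximum is 30. Nine other items at 3 plus item 7 at 3 gives 9 × 3 + 3 = 30. This reproduces under the SAP rule and under the form's routing, so a range check would not reveal the problem.

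**Which part is 7a.** *No* and *Not relevant* are answers to the first part only, so 7a in the rule must be the first question and 7b the follow-up, even though the listing note labels the two parts Q7 and Q7a.

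**Score by answer path.** Error = SAP rule − form routing.

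| Answer to item 7 | Form routing, SAP scores | SAP rule | Error |
|---|---|---|---|
| Yes | 3 | 3 | 0 |
| No, A lot | 2 | 0 | −2 |
| No, A little | 1 | 0 | −1 |
| No, Not at all | 0 | 0 | 0 |
| Not relevant | 0 | 0 | 0 |

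Under the SAP rule item 7 can only be 0 or 3.

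**Change from baseline in the total.** Error in change = error at visit − error at baseline. Rows are the baseline answer, columns the answer at the visit:

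| Baseline | Yes | No, A lot | No, A little | No, Not at all | Not relevant |
|---|---|---|---|---|---|
| Yes | 0 | −2 | −1 | 0 | 0 |
| No, A lot | +2 | 0 | +1 | +2 | +2 |
| No, A little | +1 | −1 | 0 | +1 | +1 |
| No, Not at all | 0 | −2 | −1 | 0 | 0 |
| Not relevant | 0 | −2 | −1 | 0 | 0 |

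The counts are −2 in 3 cells, −1 in 4, 0 in 11, +1 in 4 and +2 in 3, so 14 of 25 answer pairs give a wrong change. This counts answer combinations. It is not an error rate among subjects.

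Two examples, where a negative change is improvement:
- *Yes* to *No, A lot*: SAP 0 − 3 = −3; form 2 − 3 = −1. Improvement is overstated by 2.
- *No, A lot* to *No, Not at all*: SAP 0 − 0 = 0; form 0 − 2 = −2. Improvement is understated by 2.

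**Group means.** If a share p answers *No, A lot* and a share q answers *No, A little* at a visit, the mean total is too low by 2p + q. The documents give neither share. As an assumption only, p from 5% to 20% and q from 10% to 30% gives 2(0.05) + 0.10 = 0.2 up to 2(0.20) + 0.30 = 0.7 points. The error in mean change depends on how p and q move between baseline and the visit in each arm, so it has no predictable sign.

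**The case against.** The strongest reply is that this is a drafting slip with little consequence. The DLQI is summarised descriptively on observed cases, with no test and no imputation, and a programmer who knows the instrument would probably score it properly. The first part is true and limits the weight of the point. The second is not safe: the Work and School shell follows the faulty rule by leaving out the follow-up answers, and Protocol 8.10 says the SAP prevails where the two documents differ, so the form does not correct the rule by default.

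Several narrower objections have merit:
- The SAP gives no explicit score for *No* on 7a; the 0 is implied. A programmer could instead treat the item as unanswered. That also scores 0, but it would count toward the rule that makes the total missing when two questions are unanswered. Both readings lose the 2 and the 1.
- The protocol contains no DLQI scoring rule, so this is not an undeclared departure from it. The conflict is between the SAP sentence, the SAP's own answer table and the form.
- Showing Work and School as answer categories is a consistent design, since the other single-item domain, Treatment, is shown the same way. But the Treatment shell lists every graded answer, and the Work and School shell does not.
- No change from baseline is laid out for Work and School, so the change errors above concern the DLQI total only.

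**Conclusion.** The concern holds. The rule as written gives wrong DLQI totals for two of the five valid item-7 answers, by 2 and 1 points out of 30, and makes the Work and School value in Listing 16.2.6.9.2 too low for the same subjects. Change in the total can be wrong by up to 2 points either way. Neither the size nor the direction of the effect on arm means or between-arm differences can be derived from the documents. The conclusion rests on the routing printed in Protocol Appendix 5 and the scores in the SAP's own table. It should be fixed, but it does not touch the co-primary endpoints, power or Type I error.

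**What to change.** Replace the sentence in SAP 12.7.3 by a rule for each answer to 7a:
- *Yes*: item 7 scores 3; 7b is ignored.
- *No*: item 7 takes the 7b score (*A lot* 2, *A little* 1, *Not at all* 0).
- *Not relevant*: item 7 scores 0; 7b is ignored.

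State whether *No* with 7b blank counts as an unanswered question for the missing-total rule. Use one set of labels, since 12.7.3 writes 7a/7b and the listing note writes Q7/Q7a. In the Work and School shell of Table 14.2.3.2.2, add the follow-up answers as categories or show the 0 to 3 score.

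The cost is one or two sentences, one derivation line and one table shell. The printed form collects the follow-up answer, so no new data should be needed. Listing 16.2.6.9.1 has a single Q7 column and the electronic questionnaire is not shown, so confirm that both parts are stored separately.

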Appendix 8 Work Productivity and Activity Impairment Questionnaire: Psoriasis V2.0 (WPAI:PSO)

The following questions ask about the effect of your psoriasis on your ability to work and perform regular activities. *Please fill in the blanks or circle a number, as indicated.*

1. Are you currently employed (working for pay)? _____ NO ___ YES
If NO, check "NO" and skip to question 6.

The next questions are about the **past seven days**, not including today.

2. During the past seven days, how many hours did you miss from work because of problems associated with your psoriasis? *Include hours you missed on sick days, times you went in late, left early, etc., because of your psoriasis. Do not include time you missed to participate in this study.*

_____ HOURS

3. During the past seven days, how many hours did you miss from work because of any other reason, such as vacation, holidays, time off to participate in this study?

_____ HOURS

[figure not shown]
4. During the past seven days, how many hours did you actually work?

_____ HOURS *(If "0", skip to question 6.)*

5. During the past seven days, how much did your psoriasis affect your productivity while you were working?

Think about days you were limited in the amount or kind of work you could do, days you accomplished less than you would like, or days you could not do your work as carefully as usual. If psoriasis affected your work only a little, choose a low number. Choose a high number if psoriasis affected your work a great deal.

Consider only how much psoriasis affected productivity while you were working.

[figure not shown]

CIRCLE A NUMBER

6. During the past seven days, how much did your psoriasis affect your ability to do your regular daily activities, other than work at a job?

By regular activities, we mean the usual activities you do, such as work around the house, shopping, childcare, exercising, studying, etc. Think about times you were limited in the amount or kind of activities you could do and times you accomplished less than you would like. If psoriasis affected your activities only a little, choose a low number. Choose a high number if psoriasis affected your activities a great deal.

Consider only how much psoriasis affected your ability to do your regular daily activities, other than work at a job.

CIRCLE A NUMBER

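### The SAP leaves out of WPAI overall work impairment any employed subject with psoriasis-related hours missed and no hours worked, although its own formula scores that subject exactly 100%

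*SAP*

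**What the plan says.** SAP 12.7.3 derives four WPAI:PSO percentages and notes that they run with "higher numbers indicating greater impairment and less productivity". Three of its rules, and one instruction on the form, matter here.

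- **Work time missed** is 100 × Q2/(Q2 + Q4). The population is set by employment alone: "The percent work time missed due to psoriasis will be summarized for all subjects who answer “Yes” to Question 1".
- **Impairment while working** is 100 × Q5/10, limited to subjects whose "response to Question 4 is greater than zero".
- **Overall work impairment** is 100 × {Q2/(Q2 + Q4) + [1 − Q2/(Q2 + Q4)] × Q5/10}, limited to "subjects who answer “Yes” to Question 1 and response >0 to Question 4".
- **The form** (Protocol Appendix 8) asks in Q2 "how many hours did you miss from work because of problems associated with your psoriasis", in Q3 for hours missed for any other reason, and in Q4 for hours actually worked. After Q4 it instructs "If '0', skip to question 6", so Q5 is blank by design when no hours were worked.

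A general rule closes the SAP's WPAI text: "Any of the impairment percentage will be considered as missing if the contributing question is missing". SAP Section 9 provides no imputation for QoL endpoints and lists WPAI:PSO as observed cases in the FAS. SAP 12.8.3 makes the analysis descriptive. SAP Section 13 records no reason for the hours-worked condition on overall impairment.

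**The concern.** The hours-worked condition belongs with impairment while working, because a subject who did not work has no at-work productivity to rate. Overall work impairment is different. It combines absence with impairment at work, so complete absence because of psoriasis is its extreme value, not an undefined one.

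Two rules keep such a subject out. The explicit one is Q4 > 0. The second is the missing-item rule, if a Q5 left blank by the form's instruction counts as a missing contributing question. Deleting the first condition alone might therefore not restore the subject.

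At stake is the level of one reported QoL percentage at each visit, and its change from baseline at Weeks 12, 16 and 24 (Protocol 4.2.2, SAP Table 14.2.3.4). A subject fully off work at baseline who later returns has no change score on this measure. Neither does a subject who was working at baseline and is fully off work later.

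**Working it through.** The plan states no figure to reproduce, so the check evaluates the SAP's own formulas (SAP 12.7.3) against its own eligibility rules.

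**1. Employed, Q2 = 40, Q4 = 0**
- Work time missed = 100 × 40/(40 + 0) = 100%.
- Overall impairment = 100 × {40/40 + (1 − 40/40) × Q5/10} = 100 × {1 + 0 × Q5/10} = 100%. Evaluated at every Q5 from 0 to 10, the result is 100.0 each time. Q5 has zero weight, so its absence leaves nothing undetermined.
- SAP eligibility: Q4 is not above 0, so the subject is not summarised.

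The same holds for any Q2 > 0 with Q4 = 0, because Q2/(Q2 + 0) = 1.

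**2. One hour worked: Q2 = 39, Q4 = 1**
- Overall impairment = 100 × {39/40 + (1/40) × Q5/10}, which is 97.5% (Q5 = 0), 98.75% (Q5 = 5) or 100% (Q5 = 10).
- This subject is included. One hour of work separates a score of at least 97.5% from exclusion.

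**3. Employed, Q2 = 0, Q4 = 0**
- Both ratios are 0/0. Exclusion from overall impairment is right here. For work time missed the SAP gives no rule for this case.

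**4. Direction**
- Every excluded subject with a computable score sits at 100%. With n employed subjects, k of them at 100% and the others averaging m, the full mean is m + (k/n)(100 − m), while the SAP reports m. The difference is never negative.

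**5. Size, on assumed inputs.** The documents give neither the number employed, nor k, nor m. Take n = 60 and m = 25, so each excluded subject adds 75/60 = 1.25 points. For the change column, suppose the others improve by 10 points and the k subjects, off work at baseline, improve by 80.

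| k | Mean with them | Mean reported | Change with them | Change reported |
|---|---|---|---|---|
| 0 | 25.0 | 25.0 | −10.0 | −10.0 |
| 1 | 26.3 | 25.0 | −11.2 | −10.0 |
| 3 | 28.8 | 25.0 | −13.5 | −10.0 |
| 5 | 31.3 | 25.0 | −15.8 | −10.0 |

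For k = 3, the change is (57 × −10 + 3 × −80)/60 = −810/60 = −13.5.

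The change can also be distorted the other way. If instead 3 of the 60 go from 25% to fully off work (+75 points), the change with them is (57 × −10 + 3 × 75)/60 = −345/60 = −5.75, against −10 reported.

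Other assumed inputs move the size: with n = 30 and m = 20, each excluded subject adds 80/30 = 2.67 points.

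**The case against.** The strongest objection is that little depends on this. WPAI:PSO is outside the secondary efficacy list in SAP 12.7.2, has no test or model, and overall impairment is one of four percentages in one table. That stands: no efficacy conclusion in the plan rests on it.

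A reader might infer that the subject disappears from the WPAI results, or that the largest improvements go unseen. The documents do not support that. Work time missed has no hours-worked condition, so the subject is scored 100% there and contributes a change on returning to work. The form also sends the subject on to Q6, so activity impairment is kept. The loss is confined to overall work impairment.

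A reader might also infer that the rule removes only the most impaired subjects, or only those whose whole week was lost to psoriasis. Neither follows. Subjects with Q2 = Q4 = 0, such as those on a week's vacation, are also removed, and correctly. And because Q3 is not in the formula, a subject with Q2 = 1, Q3 = 39 and Q4 = 0 also computes to 100%. The accurate statement is narrower: among computable scores, only scale-maximum ones are dropped. The SAP already accepts the Q3 limitation for work time missed.

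The documents give no basis for a bias toward a particular arm either. Baseline exclusions precede treatment, and losses in the change score can run in either direction.

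Finally, whether a Q5 skipped by instruction is a missing contributing question is a matter of reading. The explicit Q4 > 0 condition excludes the subject regardless, so the point does not depend on it.

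**Conclusion.** The point holds as a scoring error of low consequence. The SAP excludes subjects whose overall work impairment its own formula fixes at 100%, while scoring them 100% on work time missed. In Listing 16.2.6.11 such a subject would show 100% for one measure and no value for the other at the same visit. No other part of the SAP, including the shells and listings, restores the score.

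The direction at any one visit follows from the algebra: mean overall impairment can be understated but not overstated. The direction for change from baseline is not fixed. The size is unknown. It depends on the number of employed subjects with Q2 > 0 and Q4 = 0, which the documents do not give and which may be zero. The 1.25 points per subject rests entirely on the assumed 60 employed subjects and 25% mean. The co-primary and secondary efficacy analyses are unaffected.

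**What to change.** Replace the eligibility condition for percent overall work impairment in SAP 12.7.3 with rules covering each case:

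- Summarise it for subjects with Q1 = Yes, Q2 and Q4 both non-missing, and Q2 + Q4 > 0.
- If Q4 = 0 and Q2 > 0, set it to 100% and do not require Q5. State that this case is exempt from the missing-item rule.
- If Q4 > 0, use the stated formula, and set the score to missing when Q5 is missing.
- If Q2 = Q4 = 0, set both overall work impairment and work time missed to missing.

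Leave the hours-worked condition on impairment while working as it is. List the subjects with Q4 = 0 and Q2 > 0 together with their Q2 and Q3 hours, so that a reader can tell a week lost to psoriasis from one lost mainly to other causes. Listing 16.2.6.11 currently shows only the derived percentages.

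The cost is a few lines of SAP text, a small change to the derivation code and an addition to one listing. All the items are already collected on the form.
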